5.2.4. Duration of a Treatment Regimen

The duration of a given treatment regimen is the time period from the start of the treatment regimen to the end of that treatment regimen. The duration will stop and start for each treatment

	Statistical Analysis Plan	Final v1.0
---	----------------------------------	-------------------

regimen change. If a patient is treated in a given treatment regimen more than once, the total durations in the same treatment regimen will be added together. For example, if a patient is treated with the prophylactic regimen and then undergoes surgery and then goes back to the prophylactic regimen, then his total duration in the prophylactic regimen will be the sum of the two durations in the prophylactic regimen. Further details will be provided for individual analysis where needed.

The total duration of time allocated to each treatment regimen will be calculated in minutes and converted to days as the number of minutes divided by 1440.

5.3. Data Summaries

5.3.1. Continuous Variables

Continuous variables (e.g., age) will be summarized using the following standard summary statistics: number of patients (n), mean, standard deviation (SD), median, minimum value (min), and maximum value (max). In addition, if specified in the analysis table shells for this study, the 25th and 75th percentiles will also be presented. Summary statistics, excluding minimum and maximum, will be presented to one decimal place beyond that with which the study data were collected. For example, for data collected to no decimal place (e.g., 20 EDs), the mean and median will be presented to 1 decimal place and the SD to 2 decimal places; for data collected to 1 decimal place, the mean and median will be presented to 2 decimal places and the SD to 3 decimal places; and so forth. Minimum and maximum will be displayed as reported in the source data. If the measurements are transformed, then the mean, median, SD, minimum, maximum of the transformed measurements will be presented with the appropriate precision.

Unless impractical within a table of analysis results, statistics will be aligned by the decimal place in the summary tables (even if not displayed in this manner in the table shells).

5.3.2. Categorical Variables

Categorical variables (e.g., ITI response) will be summarized using counts and percentages. All percentages will be rounded and presented to one decimal place, unless otherwise specified in the Statistical Programming Specifications for the study. The denominator for calculating percentages will depend on the variable to be summarized. For example, the denominator for calculating percentage of patients with any adverse event will be the Safety Analysis Set, which is number of patients dosed with rFVIIIFc.

5.3.3. Event Time Variables

The only such variable being analysed in this study is the time to inhibitor (see Section [5.1.2.4](#) for complete definition). The cumulative incidence of these inhibitors over time (EDs) will be estimated using the Kaplan-Meier method and presented graphically.

5.4. Study Periods

5.4.1. Screening Period

The screening period starts after a patient signs the study consent form and ends immediately prior to administration of the first dose of study drug rFVIII Fc.

5.4.2. Efficacy Period

The efficacy period will be used for the evaluation of efficacy and health outcome endpoints. For a patient to have an evaluable efficacy period over the duration of study, he must have at least 1 day of treatment for an episodic regimen or at least 2 prophylactic injections for prophylactic regimens.

The start and end, and the total duration of the efficacy period for a given treatment regimen is the same as the start and end, and the total duration of that treatment regimen defined in Section 5.2.4 with the exceptions described in the following two subsections. The start of the efficacy period for each patient is the start of their first treatment regimen and the end is the end of their last.

5.4.2.1. Adjustments Due to Surgical/Rehabilitation Periods

For analysis purposes, the efficacy period for a given treatment regimen will be adjusted for all surgical/rehabilitation periods (major and minor). The start and end of the efficacy period for a given treatment regimen are adjusted as follows:

- For patients on a prophylactic regimen before the start of a surgical/rehabilitation period, the efficacy period for the prophylactic regimen continues up to the last dose (for prophylaxis or bleeding) before the start of the surgical/rehabilitation period.
- For patients on the episodic regimen before the start of a surgical/rehabilitation period, the efficacy period for the episodic regimen continues up to 1 minute before the start of a surgical/rehabilitation period.
- For patients on a prophylactic regimen following the end of a surgical/rehabilitation period, the efficacy period for the prophylactic regimen starts or re-starts (depending on whether there is a treatment regimen change during the surgical/rehabilitation period) at the first prophylactic dose following the end of the surgical/rehabilitation period.
- For patients on the episodic regimen following the end of a surgical/rehabilitation period, the efficacy period for the episodic regimen starts or re-starts (depending on whether there is a treatment regimen change during the surgical/rehabilitation period) at 00:01 on the day following the end of the surgical/ rehabilitation period.

Start and end dates/times for the efficacy period for given treatment regimens and treatment regimen changes will be adjusted for each surgery (major or minor) as necessary.

For patients on a prophylactic regimen before the start of a surgical/rehabilitation period, the interval of time between the last dose before a surgical/rehabilitation period and the start of the surgical/rehabilitation period will not be attributed to the efficacy period for the prophylactic regimen. By definition, there should not be any treated bleeding episodes in this interval of time.

For patients on a prophylactic regimen following the end of a surgical/rehabilitation period, bleeding episodes that occur after discharge from a rehabilitation facility but before the next prophylactic dose will be attributed to the surgical/rehabilitation period and hence not counted towards the annualized bleeding rate (ABR).

5.4.2.2. Adjustments Due to Large Injection Intervals

For analysis purposes, the efficacy period will also be adjusted to account for large intervals between injections resulting from missing data. A large interval is defined as >28 days between any 2 adjacent rFVIIIFc injections within a prophylactic treatment regimen and any such intervals will be removed from the efficacy period. The efficacy period prior to each such interval will end at the time of the first injection of this interval and restart (or start if it is the first interval of a treatment regimen) at the time of the second injection of this interval. The efficacy period will be adjusted for each identified interval that is not within a surgical/rehabilitation period. This algorithm applies only to prophylactic regimens and no adjustment for large injection intervals will be made for episodic treatment regimens.

5.4.3. Surgical/Rehabilitation Period

The broadest span of time for the surgical/rehabilitation period is from the first dose of rFVIIIFc given for the surgery (i.e., the pre-surgery dose) up to 1 minute before the first regular prophylactic dose after the last day of postoperative care/rehabilitation. Since not all patients will have these events, specific considerations for the start and end of the surgical/rehabilitation period are as follows:

Start of the surgical/rehabilitation period:

- If there is more than one pre-surgical dose then the first one should be selected (a pre-surgical dose can be administered the day before the surgery).
- If there is no pre-surgical dose but there was a prophylactic dose the day before surgery, this prophylactic dose should be selected.
- If there is no pre-surgical dose or a prophylactic dose the day before surgery then select the start date/time of the surgery. If the time was not recorded then select the date and impute 00:01 for the time.

End of the surgical/rehabilitation period:

- 1 minute before the first prophylactic dose on or after the last date among the dates for discharge from the hospital, post-operative visit 1, post-operative visit 2, and the end of rehabilitation.
- If all of the dates mentioned above are missing, then select the first prophylactic dose after the date/time for the end of surgery. If the surgery time was not recorded then select the surgery date and impute 23:59 for the time. If the end date of the surgery is missing then select the start date of the surgery and impute 23:59 for the time.

- If there are no prophylactic doses following the latter of the 5 dates mentioned above, then select the latter of the dates and impute 23:59 for the time if otherwise there is no time associated with the given date (e.g., the patient completed the surgical/rehabilitation period but received no further prophylactic doses).
- If the overall end of study is declared while the patient is still in the surgical/rehabilitation period then select the date of the end-of-study visit and impute 23:59 for the time if a time is not provided.

Two exceptions are noted:

- If 2 (or more) major surgeries are performed without an intervening discharge from the hospital, then the first surgical/rehabilitation period will end 1 minute before the start of the next surgery and the second surgical/rehabilitation will end as described above.
- If minor surgery is performed during postoperative care or rehabilitation then the surgical/rehabilitation period for the minor surgery will start and end on the day of the minor surgery, at 00:01 and 23:59, respectively, if times are not otherwise provided or recorded as 00:00. The surgical/rehabilitation period for the major surgery will include the minor surgery (i.e., the surgical/rehabilitation period for the major surgery does not stop and restart around the minor surgery) and will end as otherwise defined.

Within the total surgical/rehabilitation period, the time is divided into:

- Intraoperative period: from the date/time of the pre-surgery rFVIII Fc dose to the date/time of the end of surgery.
- Postoperative care period: from the date and time plus 1 minute following the end of surgery to the last dose of rFVIII Fc given for the surgery, including doses given to prevent bleeding during the postoperative period.
- Postoperative rehabilitation period: from the date following the last day of postoperative care to the end of the surgical period as described above.

The surgical/rehabilitation period will be determined in the same manner for both major and minor surgeries.

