#### **16.2.2. General Methods of Analysis**

All efficacy endpoints are secondary. No imputation will be applied to any missing efficacy data.

CONFIDENTIAL

The information contained herein may not be used, disclosed, or published without the written consent of Bioverativ Therapeutics Inc.

The efficacy and surgical/rehabilitation periods will be defined in the statistical analysis plan (SAP) for the purpose of determining the study periods during which data will be used for select efficacy analyses. Data on bleeding and rFVIII Fc consumption will be based on the efficacy period; surgical evaluations will be based on the surgical/rehabilitation period.

Analysis of efficacy endpoints that are visit-based will include data from all study visits whether or not in the efficacy period, unless that visit is coincidental with a surgical/rehabilitation period for a major surgery, in which case it would be excluded.

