5.2.2. End Date and Time of the Last Treatment Regimen

The end of the last treatment regimen will be either:

- The date and time of the last rFVIII Fc dose for patients whose last treatment regimen was prophylaxis, ITI, or if they ended the study in a surgical/rehabilitation period
- At 23:59 on the day of the last non-safety follow-up study visit for patients whose last treatment regimen was episodic.

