5.2.3. Treatment Regimen Changes

In the following sections, new treatment regimen refers to the regimen to which the patient has changed, and the previous treatment regimen refers to the regimen immediately before the new treatment regimen. The start date and time of the new treatment regimen and the end date and time of the previous treatment regimen are defined in the following scenarios:

- From the episodic regimen to a prophylactic regimen: The prophylactic regimen starts at the date and time of the first prophylactic dose in the prophylactic regimen. The episodic regimen ends 1 minute before that. If the time of the first prophylactic dose in the prophylactic regimen is not available, the prophylactic regimen will start at 00:01 on the day of the first prophylactic dose in the prophylactic regimen, and the episodic regimen will end at 23:59 on the day prior to that.
- From the episodic regimen to an ITI regimen: The ITI regimen starts at the date and time of the first ITI dose in the ITI regimen. The episodic regimen ends 1 minute before that. If the time of the first ITI dose in the ITI regimen is not available, the ITI regimen will start at 00:01 on the day of the first ITI dose in the ITI regimen, and the episodic regimen will end at 23:59 on the day prior to that.
- From a prophylactic regimen to the ITI regimen: If there is no prophylactic dose on the day of the treatment regimen change recorded in the eCRF, the ITI regimen starts at 00:01 on the day of treatment regimen change, and the prophylactic regimen ends at 23:59 on the day prior to the day of treatment regimen change. If there is a prophylactic dose on the day of treatment regimen change, the ITI regimen starts 1 minute after that prophylactic dose, and the prophylactic regimen ends on the date and time of that prophylactic dose.
- From a ITI regimen to a prophylactic regimen (tapering): If there is no ITI dose on the day of treatment regimen change recorded in the eCRF, the prophylactic regimen starts at 00:01 on the day of treatment regimen change, and the ITI regimen ends at 23:59 on the day prior to the day of treatment regimen change. If there is an ITI dose on the day of treatment regimen change, the prophylactic regimen starts 1 minute after that dose, and the ITI regimen ends on the date and time of that dose.

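### SAP 5.4.3 runs the surgical period of a patient who returns to episodic treatment up to the later start of prophylaxis, so his post-operative episodic time leaves the episodic ABR and consumption

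*SAP*

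**What the plan says.** **End of the surgical period (SAP 5.4.3).** The main rule is "1 minute before the first prophylactic dose on or after the last date among the dates for discharge from the hospital", the two post-operative visits and the end of rehabilitation. If all those dates are missing, the first prophylactic dose after the end of surgery is used. The latest date itself closes the period only in a fallback: "If there are no prophylactic doses following the latter of the 5 dates mentioned above". The section adds: "The surgical/rehabilitation period will be determined in the same manner for both major and minor surgeries".

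**End of the episodic regimen (SAP 5.2.3).** On a switch to prophylaxis, the new regimen starts at the "first prophylactic dose in the prophylactic regimen. The episodic regimen ends 1 minute before that".

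**Restart after surgery (SAP 5.4.2.1).** "For patients on the episodic regimen following the end of a surgical/rehabilitation period, the efficacy period for the episodic regimen starts or re-starts" at 00:01 on the day after the surgical period ends. The same section removes major and minor surgical periods from the efficacy period.

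**Use.** SAP 7.4.3 (ABR) and SAP 6.6.1.4 (consumption) both divide by days in the efficacy period.

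**Surgery while episodic is foreseen.** SAP 5.4.2.1 has bullets for it. Protocol 10.2.8.2.1 allows minor surgery at any time, and 10.2.8.1 gives port placement as an example. Protocol 10.2.8.3 returns subjects to the regimen they followed before surgery.

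**The concern.** SAP 3.1.2.1 places episodic treatment before prophylaxis, and SAP 3.1.2 requires prophylaxis of all patients. A later prophylactic dose is therefore the planned course for a patient operated on while episodic. The main rule in 5.4.3 suits a patient who resumes prophylaxis after surgery. Applied to a patient who resumes episodic treatment, it classes all his ordinary follow-up from the last post-operative date to the start of prophylaxis as surgical time. Bleeds, doses and days in that interval leave the episodic efficacy period.

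Whether the interval counts then depends on a later event. SAP 5.2.2 provides for end dates "for patients whose last treatment regimen was episodic". Such a patient, with no later prophylactic dose, keeps the interval through the fallback. Under SAP 3.5 the same analyses are run at the interim and the final analysis. One patient can thus have the interval counted at the interim while still episodic, and lose it at the final once prophylaxis has begun.

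After major surgery only, the over-long period has further effects. It adds ordinary bleeds to the total per surgery (SAP 7.5.3.5) and ordinary doses to the overall consumption row (SAP 7.5.3.4). It also takes adverse events (except in the top-line table), laboratory values, vital signs and visit-based efficacy data out of the summaries (SAP 9.3, 9.4, 9.5, 7.1).

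**Working it through.** The plan states no figure on this point, so there is none to reproduce.

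**1. The date rules together.** Let P be the date and time of the first prophylactic dose of the later prophylactic regimen.

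- Surgical period ends: S = P − 1 minute (SAP 5.4.3).
- Episodic regimen ends: E = P − 1 minute (SAP 5.2.3).
- Episodic restart: R = 00:01 on the calendar day after S (SAP 5.4.2.1).
- Episodic days restored = max(0, E − R).

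Since E = S and R is later than S, the result is 0. Coding the rules for all 1,440 clock times of P gave 0 each time. If the time of the dose is missing and the date is, say, 1 June, SAP 5.2.3 ends the episodic regimen on 31 May at 23:59. The restart falls on 2 June at 00:01, and again 0 days are restored.

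**2. The same rules with no later prophylactic dose.** Assume discharge on 2 March and a last study visit on 1 September. The fallback closes the period on 2 March at 23:59, the restart is 3 March at 00:01, and 183 episodic days are restored.

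**3. Possible rescues in the text.** The large-interval adjustment in SAP 5.4.2.2 applies only to prophylaxis. The two exceptions in 5.4.3 cover repeat major surgery without discharge and minor surgery during post-operative care. A further bullet covers study end during the period. None covers this case.

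**4. Illustrative size.** All inputs here are assumptions: surgery on day 0, last post-operative date on day 7, 240 true episodic days (the 7-day surgical period already removed), and 4 bleeds.

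- ABR = bleeds ÷ days × 365.25. True value: 4 ÷ 240 × 365.25 = 6.09.
- Poisson SD of the ABR = √(6.09 ÷ (days ÷ 365.25)). At 240 days this is 3.04.

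| Prophylaxis starts | Days lost | Share of 240 | Days left | SD if bleeds are proportional to time |
|---|---|---|---|---|
| Day 30 | 30 − 7 = 23 | 9.6% | 217 | 3.20 |
| Day 90 | 90 − 7 = 83 | 34.6% | 157 | 3.76 |
| Day 180 | 180 − 7 = 173 | 72.1% | 67 | 5.76 |

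If bleeds are proportional to time, the expected ABR stays at 6.09 and only precision falls. Otherwise, with 83 days lost:

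- no bleed in the lost interval: 4 ÷ 157 × 365.25 = 9.31;
- three of the four bleeds in it: 1 ÷ 157 × 365.25 = 2.33.

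**5. Group mean.** Assume 60 episodic patients, of whom m = 1 to 5 are affected, each losing 83 days.

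- No bleeds in the interval: m × (9.31 − 6.09) ÷ 60 = +0.05 to +0.27.
- Three bleeds in the interval: m × (2.33 − 6.09) ÷ 60 = −0.06 to −0.31.

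**6. Per-surgery bleed total (major surgery only).** With proportional bleeds, the expected number of ordinary bleeds credited to one surgery is 4 × 83 ÷ 240 = 1.38 for the 83-day case.

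**The case against.** **The SAP plainly means episodic time to resume.** It has a restart bullet, says dates are adjusted as necessary, and opens 5.4.3 by noting that not every patient will have the events it describes. This shows intent, but supplies no rule that returns the days. A programmer following 5.4.3 as written gets zero.

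**An isolated prophylactic injection during episodic treatment might close the period early.** SAP 5.2.3 specifies a dose within the prophylactic regimen, while the end bullet in 5.4.3 does not. On that reading, later episodic days come back. The word regular in the opening sentence of 5.4.3 argues against it, and a patient with no such injection is not helped.

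**The protocol delegates the definition.** This stands: "The efficacy and surgical/rehabilitation periods will be defined in the statistical analysis plan (SAP". A reader might infer that the SAP breaches Protocol 10.2.8.2, where the postoperative period ends with the last dose given for the surgery. It does not, because that section does not fix the analysis periods. The defect lies between sections of the SAP.

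**The wider effects are narrower than they may look.** This also stands. A reader might infer that safety data are lost after any surgery, but those exclusions apply to major surgical periods only. Major surgery needs at least 3 prior injections (Protocol 10.2.8.2.2). In SAP 7.5.3.4 the fixed day windows are unaffected, and in 7.5.3.5 the onset windows stop at Day 28. Longer intervals therefore reach only the total bleed count and the overall consumption row.

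**The sentence in 5.4.2.1 on uncounted bleeds is limited.** It concerns patients on prophylaxis after the period, and bleeds between discharge from a rehabilitation facility and the next prophylactic dose. It should not be read as a general exclusion of post-operative episodic bleeds. The loss arises from the date rules.

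**Conclusion.** The point holds as a defect in the stated rules. For a patient who returns to episodic treatment after surgery and starts prophylaxis later, no post-operative episodic time is restored. The time he keeps depends on whether a prophylactic dose ever follows. This rests on the closing dose being the first dose of the prophylactic regimen.

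The size is unknown. The documents give neither the number of such patients nor the length of their intervals. If prophylaxis starts soon after the last post-operative date, little is lost. On the assumptions above, five affected patients of 60 move the mean episodic ABR by +0.27 to −0.31 on 6.09, about 4% to 5%.

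A reader might infer that the rule flatters the product. The documents do not support a direction: bleeds and days are dropped together, so ABR can rise, fall or stay the same. Nor is the primary endpoint touched, since SAP 9.4.3.1 keeps inhibitor tests from surgical periods. The affected endpoints are secondary and no hypothesis is tested.

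For ITI the point is only conditional. Protocol 10.2.7.2 foresees surgery during ITI, and SAP 5.4.2.1 has no ITI bullet. SAP 6.6 lists ITI apart from prophylaxis as a reason for administration, while 6.6.1.3 speaks of a daily prophylactic dose for ITI. A reader might infer that the surgical period runs until tapering. That follows only if ITI doses do not count as prophylactic, which the SAP leaves open.

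**What to change.** **Main change, SAP 5.4.3.** Add one rule. For patients on the episodic regimen after surgery, the surgical/rehabilitation period ends at 23:59 on the latest available of: end of surgery (start of surgery if the end date is missing), last dose given for the surgery, discharge, post-operative visits 1 and 2, and end of rehabilitation. This applies whether or not prophylaxis starts later. The 00:01 restart in 5.4.2.1 then works as written. Including the surgery date ensures that a minor surgery without a surgical dose, discharge date or post-operative visit still has an end.

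**ITI.** State whether ITI doses count as prophylactic doses for closing the period, and add an ITI bullet to 5.4.2.1.

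**Reconcile.** SAP 5.1.2.2 ties the last post-operative visit to return to the prophylactic regimen. Protocol 4.2.2.6 (footnote d) and 10.2.8.3 refer to the pre-surgery regimen.

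**Editorial.** SAP 6.6.1.4 describes the excluded surgical periods as major only, whereas 5.4.2.1 excludes major and minor.

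**Cost.** SAP wording and one more branch in the period derivation. The dates are already used in 5.4.3, so no new data are needed and study conduct does not change.
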